The disclosure tool includes a cartoon book, readiness and tracking tools used in clinic and a HCW training. The intervention progresses from incomplete to complete disclosure using a narrative about soldiers fighting the battle of infection as the rationale for taking medicine. This tool has been validated for use in Namibia.

The Got Transition model is based on health care perspectives of adolescents, caregivers, and providers and program evaluations in the US. It has 6 core elements that were iteratively developed and offer a standardized approach that can be used in varied settings (Table 5). The Core Elements address inter-related health systems components relevant to diverse HIV programs in Kenya. The Transition tools for the ATP include a transition flipchart, readiness assessment, and transition progress tracking tool. In addition, the study team will develop training materials to support the implementation of the transition tools.

Table 5: Core elements of the Got Transition Program

6 Core Elements of Got Transition Program	
	Selected key concepts
Transition policy	Develop clinic policy on transition Educate and post policy
Transition tracking and monitoring	Criteria for identifying eligible adolescents Tracking registry/tool development
Transition readiness	Regular transition discussions starting age 14 Develop prioritized actions (joint adolescent/caregiver)
Transition planning	Regular planning, goals re: timing of transition
Transfer of care	Confirm date, assess self-care readiness
Transfer completion	Elicit feedback regarding transfer, follow-up retention

The validated Namibia booklet and the Got Transition tool can be found in the appendices.

Each clinic team in the intervention sites will implement the tools guided by the study team with twice-monthly check-ins and evaluation. The twice-monthly check-ins will use modified PDSA cycle materials to facilitate feedback and adaptations to optimize ATP implementation.

The study will aim to optimize implementation of ATP over a 6-month period at each intervention site with continued clinic support throughout the course of implementation and measure the effect of the well-implemented ATP on transition outcomes over a 2-year period.

SECTION 7: STUDY PROCEDURES

COVID-19 ADAPTED STUDY PROCEDURES

As a result of the COVID-19 pandemic and resultant changes to visit schedules and client contact time, we propose the following changes to study procedures during the pandemic period:

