Focus group discussions and interviews will be recorded and transcribed verbatim. Transcripts will be coded and thematic analysis will be conducted on the transcripts using ATLAS.ti. At least 2 researchers will independently code the data, coordinating their findings and analyses to create a comprehensive codebook and concept map. Themes related to how to culturally adapt and improve the described transition intervention, and how to improve clinical care for HIV-infected adolescents, will be identified and used to revise the implementation of the intervention.

Aim 3

The primary analysis will be an intent-to-treat (ITT) analysis.

We will use generalized estimating equations (GEE) clustered on facility level to compare differences in age-appropriate disclosure and change in transition readiness over time between control and intervention communities during baseline and intervention periods. In order to decrease variability between our sites and increase precision of our outcome measures, we will control for baseline adolescent disclosure and transition proportions in our models. We hypothesize that the increases in disclosure and transition proportions between the baseline and intervention periods will be greater among intervention than control facilities.

The first 6 months of the intervention will be considered a “catch up” period; while outcomes will be compared during the full study period, a sub-group analysis is planned for the first 6 months to see if the effect of the intervention is greater during the “catch-up” period.

Focus group discussions and interviews will be recorded and transcribed verbatim. Transcripts will be coded and thematic analysis will be conducted on the transcripts using ATLAS.ti. At least 2 researchers will independently code the data, coordinating their findings and analyses to create a comprehensive codebook and concept map. Themes related to implementation acceptability, feasibility, appropriateness and challenges and successes will be identified. Proportions satisfied with the transition and disclosure process will be compared between the 2 arms.

SECTION 12: ETHICS/PROTECTION OF STUDY PARTICIPANTS

COVID-19 ADAPTED STUDY PROCEDURES

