Recruitment Scripts:

Study Activity	Recruitment Script
Aim 1`	
Facility Survey	Facility Survey Recruitment Script
Aim 2	
Adolescents in HIV care (48 not completed transition, 48 transitioned)	NA
	Caregiver recruitment script for adolescent IDI and FGD
	Adolescent recruitment script
Caregivers	Caregiver recruitment script
Policy makers	Policy maker/Admin/HCW recruitment script
HCW/Administrator	Policy maker/Admin/HCW recruitment script
Working group	HCW recruitment script for Workshop
Aim 3	
Pre-Trial surveys	Adolescent Recruitment Script*
Implementation Activities	HCW IS Activities Recruitment Script
Post-trial IDI	NA
	Adolescent recruitment script*
	Caregiver recruitment script*
	HCW recruitment script*
Implementation FGDs	HCW FGD Recruitment Script
Transition readiness	Adolescent recruitment script*
Disclosure readiness	Caregiver recruitment script
Post-trial surveys	Adolescent recruitment script*
	HCW recruitment script*

*Same as aim 2 document

ATTACH STUDY ANALYSIS PLAN (Finalized 2.13.2020)

SUMMARY

Study Purpose: To determine whether an adolescent transition package (with transition and disclosure tools) improves **mean transition readiness** among HIV positive adolescents in care in Kenya.

Study Design: Cluster randomized trial

Study Population and Sites:

Population:

- HIV-positive adolescents and youth between the ages of 10 and 24

Sites:

- 20 HIV clinics in Nairobi, Nakuru, Homabay and Kajiado, Kenya

Study Duration: Estimated 18 months total (enrollment and 1-year follow-up)

Randomization: 10 clinics randomized to intervention sites and 10 to control.

Intervention:

Adolescent Transition Package (ATP): The ATP will consist of a validated disclosure booklet and disclosure tracking tool, and a HCW administered transition booklet and transition tracking logs, implemented in intervention sites. HCW in intervention sites will be trained on implementation of the ATP with continued support for the clinic in the first 3 months of the intervention. In control sites, parallel data collection for primary outcomes will be conducted.

Primary endpoints: Transition readiness

Secondary endpoints: Overall clinic retention and overall viral suppression

Exploratory outcome: % with full disclosure, Time to full disclosure, Post transition retention

DATA ANALYSIS

Primary outcome: transition readiness among HIV positive adolescents age 15-24

- a. Transition readiness score overall (all domains)
- b. Treatment literacy readiness score

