- c. Self-management readiness score
- d. Communication readiness score
- e. Support readiness score

Analysis

Primary analysis ITT: Mixed effects linear regression to compare transition readiness scores (overall and by domain) over time in control and intervention sites with adjustment for multiple testing (Benjamin-Hochberg method).

Time points: Enrollment, month 6, month 12

Sample size and power table

Assumptions: 80% power, alpha 0.05, ICC 0.2, average cluster size of 50

Mean difference	SD	Number of Clusters per Arm
0.5	1	4
0.5	2	15
1.0	2	4
1.0	3	9
1.5	3	4
1.5	4	7
2.0	5	6
2.0	6	9

Secondary outcomes

- a. Overall retention in 10-24 year olds: defined as proportion of 10-24 year olds completing visits within 6 months of last visit
- b. Overall viral suppression: defined as proportion of 10-24 year olds with viral load of less than 1000 copies per ml after at least 6 months of ART

Analysis

Overall retention/suppression: Generalized estimating equations (GEE) to compare retention and viral suppression in intervention and control sites

Time-points: Baseline, month 6, month 12

Minimum detectable differences in proportions with outcomes

Assumption: 80% power, alpha 0.05, ICC 0.2, 10 clusters per arm, average cluster size of 50

Proportion with outcome in arm 1	Proportion with outcome in arm 2
0.2	0.31
0.3	0.44
0.4	0.56

0.5	0.69
0.6	0.81
0.7	0.93

Exploratory analyses

1. Post-transition retention defined as completing and adult clinic visit day after transfer to adult services and at least 1 other visit within 6 months of the adult visit (total of 2 visits):
Analysis: GEE to compare post-transition retention in intervention and control sites
2. Principal components analysis to identify the most representative components of data in the 4 domains of the readiness assessment checklist (HIV treatment literacy (Q 1-5), self-management (Q6, 7, 9-14, communication Q16-19, support 20-22) and then factor analysis to determine the most important components.
3. Proportion of children with full disclosure and time to full disclosure. Children who do not know their HIV status from HCW assessment. Child will be asked why they are taking medicine; if they report they have HIV they have reached full disclosure. If they mention any other illness or other responses they will not have reached full disclosure.
End point: Child says they have HIV in response to the question “why are you taking your medicine”
Analysis: Descriptive %, time to full disclosure

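### The plan asks whether the ATP effect is greater in the 6-month catch-up period but specifies no estimate for the later period and no early-versus-later contrast

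*Combined protocol and SAP*

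**What the plan says.** Protocol Section 3 (Study Outcomes, Aim 3) and Section 11b (Overview of analysis plan, Aim 3) carry the same sentence, which treats the first 6 months of the intervention as a catch-up period. The main comparison covers the whole study: "while outcomes will be compared during the full study period". For the early months the sentence adds that "a sub-group analysis is planned for the first 6 months to see if the effect of the intervention is greater" at that stage. No estimator is named.

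The protocol's model in Section 11b is a GEE clustered on facility that compares the arms "between control and intervention communities during baseline and intervention periods". It does not divide the intervention period.

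The SAP's primary analysis is described as "Mixed effects linear regression to compare transition readiness scores (overall and by domain) over time in control and intervention sites", with "Time points: Enrollment, month 6, month 12". It does not say whether time is categorical, whether it interacts with arm, or which contrast over time is of interest. The catch-up period appears nowhere among the SAP's primary, secondary or exploratory analyses.

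The length of follow-up also differs. Protocol Section 6 intends to "measure the effect of the well-implemented ATP on transition outcomes over a 2-year period", while the SAP Summary gives "Estimated 18 months total (enrollment and 1-year follow-up").

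**The concern.** Whether an effect is greater in one period than in another is a question about a difference between two effects. The plan names an analysis of the early period and an analysis of the whole, but none of the later period and none of the difference. An analysis of the first 6 months by itself tests whether the early effect differs from zero. It gives the same answer whether the later effect is larger, equal or absent.

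The answer has practical weight. In the protocol the first 6 months are the phase of intensive clinic support and optimisation. If the benefit is concentrated there, that bears on how the package would perform once support eases. With no contrast fixed in advance, an early estimate that happens to be significant, or to look larger, could be reported as evidence of a catch-up effect.

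**Working it through.** The documents give no sample size, power or alpha for the catch-up question, so there is no planned figure to reproduce. The check has three parts.

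**1. What each planned analysis estimates.** Let E1 be the arm effect in months 0–6 and E2 the arm effect after month 6.

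- First-6-months sub-group (protocol Sections 3 and 11b): estimates E1.
- Full-period comparison (same sections): estimates a mixture of E1 and E2.
- Protocol GEE: baseline against intervention period, with no early/late term.
- SAP mixed model: scores over time, with no stated contrast of months 0–6 and 6–12.

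The quantity that answers the question is E1 − E2. None of the four is specified to deliver it.

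**2. Whether early against full period can stand in for it.** This depends on how the effect is defined.

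- If the full-period effect is a weighted average, Full = w·E1 + (1 − w)·E2, then E1 − Full = (1 − w)(E1 − E2). The sign is right and the size is reduced.
- If the effect is change from enrollment, as for readiness, Full = E1 + E2, so E1 − Full = −E2. This says nothing about E1.
- For disclosure, children disclosed early are no longer at risk later, so no fixed weight applies.

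The plan does not say which definition holds. In every case the two estimates share data, so a standard error for their difference needs a joint fit or resampling of clinics. The plan gives neither.

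**3. Illustration of the risk.** Assumptions not in the documents: normal estimates, equal standard errors in the two periods, two-sided 0.05, 80% power for an effect δ within each period, and correlation ρ between the two period estimates. Then δ/SE = 1.96 + 0.84 = 2.80.

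With E1 = E2 = δ, that is, no catch-up effect:

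- The early-only test is significant in 80% of trials.
- Early significant and later not: 0.80 × 0.20 = 16% at ρ = 0, and 11% at ρ = 0.5 (simulated).
- A direct contrast of E1 and E2 is significant in 5% of trials, 2.5% in the direction of a greater early effect.

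Power of the direct contrast, with SE(E1 − E2) = SE·√(2(1 − ρ)) and power = Φ(D/SE(E1 − E2) − 1.96) for a true early–later difference D:

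| ρ | √(2(1 − ρ)) | D = δ | D = δ/2 |
|---|---|---|---|
| −0.5 | 1.73 | 37% | 12% |
| 0 | 1.41 | 51% | 17% |
| 0.3 | 1.18 | 66% | 22% |
| 0.5 | 1.00 | 80% | 29% |
| 0.7 | 0.77 | 95% | 44% |

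For example, at ρ = 0 and D = δ: 2.80/1.41 − 1.96 = 0.02, and Φ(0.02) = 51%.

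The row ρ = −0.5 matters for readiness gains. The gains from 0 to 6 and from 6 to 12 months share the month-6 score with opposite signs. If the three scores are equally correlated (r), the covariance of the gains is −(1 − r) and each variance is 2(1 − r), in units of the score variance, so ρ = −0.5.

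**The case against.** Section 11b is an overview. A sub-group analysis can be carried out with an interaction term, and a question about a greater effect implies a comparison. A reader might infer that the plan confines itself to the first 6 months and so is incapable of answering. The text does not go that far: it leaves the method open, and it nowhere says that a significant early result will be read against a non-significant full-period one.

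A reader might also infer that the early-minus-full difference has no valid standard error. That is too strong, since a joint model or a clinic-level bootstrap would supply one. Nor can one say that this difference recovers a set fraction of the early–later contrast, such as half over 12 months or three quarters over 24. Those fractions hold only for time-averaged effects, and readiness change and cumulative disclosure are not of that kind.

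Finally, the SAP's mixed model could yield the contrast if time is categorical and interacts with arm, and the SAP may have dropped the catch-up question on purpose.

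These points limit the claim but do not remove it. The protocol asks a comparative question twice, and no text in either document specifies the later effect, the contrast or its interval. If the analysis was dropped, neither document says so.

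**Conclusion.** The concern holds in limited form. As written, neither the sub-group result nor an informal comparison with the overlapping full-period result would show that the early effect is greater, and the contrast that would show it is not specified. The 80%, 16% and 11% figures illustrate the risk under the assumptions stated with them; they are not estimates for this trial.

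A reader might infer that the trial's main conclusions are in doubt. They are not: this is a supporting analysis that appears only in the protocol, and no primary or secondary result or sample size depends on it. It is a cheap improvement.

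**What to change.** Either add the analysis to the SAP or state in the protocol that it has been dropped. If it is kept:

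- In the existing clustered model, include arm-by-period terms (months 0–6 against after month 6). Report the difference between the two arm effects with its confidence interval.
- Define the effects on a scale that separates the periods: for readiness, the gain within each period; for disclosure, new full disclosures among those still undisclosed at the start of the period. Children undisclosed at month 6 are selected by what happened earlier, so the later disclosure comparison is not fully protected by randomisation and should be read with that caution.
- State when the period starts and ends. The protocol counts from the start of the intervention, whereas the SAP's time points run from enrollment, and 18 months in total less 1 year of follow-up leaves up to 6 months of enrollment. State also whether the later period follows the protocol's 2 years or the SAP's 12 months.
- Label the result exploratory and state that power is low with 20 clinics, so that the interval carries the message and a non-significant contrast is not read as equal effects.

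The cost is one additional model term and a paragraph of text. No new data are needed: SAP Appendix 1 already schedules readiness at months 0, 6 and 12 and the disclosure checklist every 3 months. The drawback is an interval that may be too wide to settle the question.

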Adolescents participating in focus group discussions must be aged 14-24 years old and must know that they are HIV positive and have attended HIV care for at least 1 year. Caregivers participating in focus group discussions must be ≥ 18 years of age and the primary caregiver of an adolescent ages 14-24 years old. HCWs participating in interviews should be employed at trial sites for at least 6 months prior to the interview date and provide clinical or counselling services to HIV-infected adolescents. Policy makers must be ≥ 18 years of age and employed at the national, county or HIV implementing partner (NGOs or Universities) organization in a policy making role. Hospital administrators must be ≥ 18 years of age and serve at an administrative and local policy making level within facilities.

Aim 3:

To participate in the RCT, facility leadership must be willing to implement the intervention. Clinics already actively using transition or disclosure tools will be excluded. Child and adolescent records will be abstracted for all 6-24 year olds enrolled in HIV care at participating facilities. In addition, every 6 months, we will collect readiness assessment data from adolescents and young adults up to the age of 24 years who have attained full disclosure and caregivers of children and adolescents who have not yet reached full disclosure. Adolescents and/or caregivers will give consent and/or assent to participate in readiness assessments. HCWs who complete interviews, focus groups or surveys must be ≥ 18 years of age and employed at trial sites or by the ATTACH study during the intervention period and providing clinical services or performing study activities with adolescents. Adolescents who complete the interviews must be ≥ 18 years or must have caregiver consent to participate if less than 18 years. Adolescents who participate in interviews must know their HIV status. Adolescents who complete the pre-trial and post-trial surveys must

give oral consent or assent for participation, and be between the ages of 12 and 24 years of age and know their HIV status.

5d. Site/participant exclusion criteria

Facilities will be excluded if they do not meet inclusion criteria. A facility may also be excluded if anything would prevent the complete conduct of the intervention at that site and/or the collection of outcome measures. An example of this would be if a separate transition intervention was being developed at the site concurrent to our study.

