As a result of the COVID-19 pandemic, some activities will be move to being offered by phone. For adolescents, study activities conducted by phone pose potential additional risks of inadvertent disclosure of adolescent HIV status for participating adolescents. However, healthcare providers already routinely call adolescents to remind them of clinic visits and support groups, and may be moving to provide more services by phone to minimize exposure at clinics during the COVID-19 pandemic. To minimize potential disclosure risks, we will first confirm that the person on the phone is the enrolled study participant. We will also ask the participant to confirm willingness to participate in phone-based activities. We are also only offering services to adolescents who know their status, as part of the inclusion criteria for enrolling in the transition intervention activities.

12a. Informed Consent Process

Clinic participation

This intervention will be at facility level therefore, we will engage with the relevant HIV care partners, county health management and facility administration teams prior to entering health facilities. Because we will be collecting routinely collected program data on adolescent retention and health outcomes, we will request a waiver of individual consent of adolescent patients for abstracting clinic records.

HCW and Policy makers and administrators

HCW participants will provide written informed consent for participation in IDIs, FGDs, implementation evaluation activities, and the working group.

For post-trial surveys among HCWs, we will request waiver of written consent as no identifying information will be collected.

Policy makers and administrators will provide written informed consent for participation in IDIs.

Adolescent patients

The consent and assent process for IDIs and FGDs by age is described below:

- 1) Adolescents ages 14-17 who come with a caregiver: Written informed consent will be sought from the caregiver and written assent will be sought from the minor. We will not enroll any adolescent between ages 14 and 17 who is unaccompanied by a caregiver.
- 2) Adolescents >18: Regardless of whether they are accompanied, adolescents will provide written informed consent.

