We anticipate that the majority of study participants will be fluent in either Kiswahili, Luo, or English or other language appropriate for where the research study is taking place. We will generate study materials specific to each of those languages. For interviews and focus group discussions, we will ensure that the interviewer is fluent in the preferred language spoken by patients at the clinic.

We will not provide interpretation services. We will require that our research coordinator(s) and qualitative study staff be fluent in English, Swahili, Luo or another local language spoken in the region where research is taking place. Only participants who understand English, Swahili and/or Luo or another language appropriate for where the study is taking place will be eligible for the study.

At least 1 study staff member will be fluent in every language we will be creating consent and other study related materials for. We will ensure that participants speak with a study staff member fluent in their preferred language when they have questions or concerns about the study.

We will work with translators/interpreters who are fluent in English, Swahili, and other relevant tribal languages to translate consent forms to the appropriate languages. Once consents are translated and transcribed into their appropriate language, they will be back translated to English by another translator/interpreter who has not seen the original English consent form to ensure that the messages and material included in the consent form is accurate. We will correct any information in the translated consents that is not correctly back translated and get approval from the ERC for all translated study materials.

12b. Participant Confidentiality

All key personnel will be trained in the Protection of Human Subjects. The field team will take every precaution to protect participants' confidentiality. To ensure confidentiality, focus group discussions and interviews will take place in rooms where the door to the room can be shut during the discussion. Only designated study staff and the individuals involved in the focus

group discussion or interview will be allowed in the room during the focus group discussion or interview.

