- *Physical:* There are no medical interventions associated with the study, therefore we anticipate no risk of serious harm to participating HCWs, adolescents, caregivers, hospital administrators or policy makers.
- *Other:* Other study risks include emotional distress associated with the sensitive nature of the disclosure process, breach of patient confidentiality during data extraction (adolescent clinic records), and fear of or actual loss of employment associated with implementing the ATP. We are not directly enrolling adolescent clients other than to take part in in-depth interviews, focus group discussions, and anonymous surveys. However, there is a possibility for social harm (depression, violence after disclosure, abandonment) related to disclosure of HIV status during clinical encounters at HIV care. However, the possibility of this social harm would exist if this intervention were not conducted. For the FGDs, it is also possible that a participant may know another member in the discussion and by participating in the discussion the other member might learn of their HIV status. We have outlined this potential risk in the consent form.

- *Other:* There is a possibility that during a clinical encounter with a HCW using the more comprehensive tools that are part of the adolescent transition package that an adolescent patient may be more comfortable disclosing that they are suffering from previously undiagnosed mental health problems such as depression. Any patients with potential mental health problems will be referred for psychosocial support at the facility or nearest referral hospital, according to standard HIV care and treatment guidelines for adolescents at that clinic and within the country.
- *Alternative treatments or procedures:* Not applicable
- *Procedures to minimize psychological risks:* All participants will be assured that their participation is voluntary and that they may withdraw from the study at any time. Study personnel experienced with adolescents will perform the disclosure intervention. Adolescent participants will be informed that they can skip any question or stop the interview, focus group or surveys at any time. We will ask all the members in focus group discussions to protect each other's privacy, and not to repeat anything that is said or learned once the discussion is over.

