- *Procedures to minimize other risks:* Study staff will be trained to take all precautions to ensure confidentiality of participation and data collected, and will have standardized operating procedures to follow to minimize the risks of a participant's loss of confidentiality. Risk of breach of confidentiality of study data is low, as all patient data collected will not include names and will be located on a password protected server, and encrypted prior to upload. Study staff will be trained in the importance of confidentiality during human participants training prior to study implementation.
- The systematic disclosure approach will minimize the possibility of involuntary disclosure of HIV status to an adolescent. Some adolescent patients are receiving HIV care and take ART (which may be called 'medicine' and not HIV medicine), but may not yet know their HIV status, because the caregiver is not ready for the child to learn this information.
- *Additional protection for children:* Additional protections will be afforded to participants in the in-depth interviews or focus group discussions. These protections will depend on adolescents' age and whether they are accompanied by a caregiver. Adolescents accompanied by caregivers will be given the option of having their caregiver present during the interview or focus group. Adolescents will also be given the opportunity to meet with a nurse counselor, or other similar staff member, if they request to see one or if the interviewer believes they should see one following the interview or focus group discussion.

Potential Benefits

- *HCWs and clinics:* HCWs in the intervention sites will receive direct and immediate benefit in receipt of disclosure skills and transition tools that may improve outcomes in their facilities.
- *Adolescent client (clinic attendees):* Adolescent clients of participating health facilities may benefit directly from the improved disclosure services and transition services they receive from trained HCWs.

Unanticipated Problems

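### Section 12c lets a caregiver sit in on an adolescent focus group, Section 12b restricts who may be in the room, and neither addresses the 4-5 other adolescents whose HIV status that caregiver would learn

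*Combined protocol and SAP*

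**What the plan says.** Two parts of Section 12 set rules on who may be present.

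- **Section 12b, Participant Confidentiality.** As a confidentiality measure, the sentence (broken across a page) reads "Only designated study staff and the individuals involved in the focus" and continues "group discussion or interview will be allowed in the room during the focus group discussion or interview". It covers focus groups and interviews, and states no exception for caregivers.
- **Section 12c, Additional protection for children.** "Adolescents accompanied by caregivers will be given the option of having their caregiver present during the interview or focus group". This also covers both settings and draws no distinction between them. The same paragraph offers adolescents access to a nurse counselor.

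The surrounding text determines how the two rules work in practice.

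- Section 5c, Aim 2: "Adolescents participating in focus group discussions must be aged 14-24 years old and must know that they are HIV positive".
- Section 12a, on interviews and focus groups: "We will not enroll any adolescent between ages 14 and 17 who is unaccompanied by a caregiver".
- Section 12c names one status risk specific to focus groups: "a participant may know another member in the discussion and by participating in the discussion the other member might learn of their HIV status". It adds that this risk is outlined in the consent form.
- The privacy request in Section 12c begins "We will ask all the members in focus group discussions to protect", and asks them to respect one another's privacy.
- Table 2 plans adolescent groups of 5-6, and Section 7b plans 16 such groups with up to 96 adolescents. Caregivers have 8 separate groups of their own.

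**The concern.** A caregiver's presence at a one-to-one interview affects only that adolescent. In a focus group it also affects the other members, because being in the group identifies a person as living with HIV. One adolescent's choice to bring a caregiver in would show the status of the rest to an adult who is neither staff nor a group member.

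The protocol itself treats this kind of harm as serious. Section 1b describes caregivers' fear of inadvertent disclosure and children losing friends and social standing once their status was known. Section 12c requires any breach of confidentiality to be reported to the university's review body within 24 hours.

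Site staff reading Sections 12b and 12c together cannot tell which rule governs a focus group. There is also a data-quality question: adolescents asked about disclosure and about moving to independent care may speak less freely with caregivers listening.

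**Working it through.** No statistical figure is at issue, so the check is a side-by-side reading with a simple count.

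**1. Do the two rules cover the same setting?** Yes. Both name focus groups and interviews. Section 12b gives a closed list of who may be in the room, and Section 12c allows a caregiver in. Neither refers to the other or states which takes precedence.

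**2. Can the option arise?** Yes. Under Section 12a every 14-17 year old must come with a caregiver, so each minor is accompanied and would be offered the choice. Section 12a also recognises that those of 18 or older may be accompanied, and the 12c wording is not limited to minors.

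**3. Does presence reveal status?** Yes. Section 5c makes knowing that one is HIV positive a condition of joining an adolescent group.

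**4. How many others per attending caregiver?**
- Group size (Table 2): 5-6.
- Consistency check with the planned total (Section 7b): 96 / 16 = 6, the upper end.
- Others in the room, leaving out the caregiver's own adolescent: 5 - 1 = 4 to 6 - 1 = 5.

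**5. Do the safeguards reach that caregiver?** Not in the protocol text. The stated risk is that another member learns a person's status, and the privacy request goes to members. A caregiver sitting in is in neither category. The text does not provide for the other adolescents to agree to that caregiver's presence.

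**6. Does the procedure text settle it?** No. Section 7b describes adolescents taking part with study staff and does not mention caregivers in the room, which fits 12b better than 12c, but it does not address the option.

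**7. Which sessions are affected?** The Aim 2 adolescent groups. The Aim 3 approach in Section 2b and the Aim 3 design text in Section 4 also mention end-of-trial focus groups with adolescents, although Table 3 and Section 7d specify only individual interviews for them. Any such groups would fall under the same two rules.

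**The case against.** The strongest reply is that there is no contradiction. Section 12b speaks of individuals involved, not of participants, and a caregiver invited under 12c may count as involved. Section 12c is also the more specific rule, written as a child protection, so it can be read as an exception to a general room rule. This stands as a possible reading, and it would remove the textual conflict. It would not remove the exposure of the other group members, which is the substantive issue.

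Other parts of the reply also stand:

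- **Consent forms.** They are not available here and may deal with caregiver presence. A reader might infer that the other adolescents never agreed to it. The documents do not support that inference.
- **Increment over existing exposure.** Under Section 7b, adolescents and their caregivers meet staff at the clinic on the day of the group. Some caregivers would see who arrives whatever 12c says, and some may already know other patients.
- **Inhibited discussion.** A reader might infer that 12c biases the Aim 2 material. That is a reasonable methodological worry, but the documents neither state nor quantify it.
- **Timing.** Section 8 places Aim 2 early, and Section 7c already names the Taking Charge transition booklet, so adaptation of the tool appears finished. Little may remain to be gained for Aim 2 itself.

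**Conclusion.** The point holds as a participant-protection issue of limited scope. Sections 12b and 12c need to be reconciled. As written, each caregiver who uses the 12c option in a focus group would hear the discussion and learn the status of 4-5 other adolescents, and the protocol's privacy request does not cover that caregiver. This rests on the group size in Table 2 and the eligibility rule in Section 5c, and it is conditional on the option being used.

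A reader might be tempted to scale this up to a trial total. With ages spread evenly within the Table 2 bands (an assumption), minors would number 48 x 4/6 = 32 in the groups not yet transitioned and 48 x 2/9 = 10.7 in the transitioned groups, about 43 in all. Full uptake would then give 43 x 5 = 215 caregiver-adolescent pairs. The documents do not support such a figure. They give neither ages within bands nor expected uptake, uptake may be nil, so the range starts at 0, accompanied adults are left out, and not every pair would be a new disclosure. Only the count per attending caregiver is usable.

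Nothing here affects the randomization, sample size, outcomes or analysis of Aim 3.

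**What to change.** - In Section 12c, limit the caregiver-present option to individual interviews, where no other adolescent is exposed.
- In Section 12b, state that interview exception explicitly and make the room rule govern any adolescent focus group, including any held at the end of the trial.
- Keep the nurse counselor offer for every adolescent.
- Extend the confidentiality request in Section 12c to any caregiver who accompanies an adolescent to the site, since a caregiver kept outside the room may still see who attends.
- Bring the consent and assent forms into line if they do not already agree.
- If the focus groups are complete, report whether any caregiver attended and in which groups.

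The cost is a few sentences of protocol text and, if needed, revised forms. The downside is small but real: a minor who wants a caregiver in the room may decline the group. Aim 2 has no individual interviews for adolescents and lists only a focus group guide for them, so no interview alternative can be promised there without adding a new procedure.
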